The Executive Committee consists of **three** members (see Appendix). All members have experience and expertise in their field of practice and in the conduct of clinical trials. Two members are experts in the care of cardiac surgical patients, and one member is a statistician.

The Executive Committee will convene to monitor the safety of the trial. This assessment will include a review of all adverse events and safety evaluation. The Executive Committee will make recommendations to the Steering Committee regarding the modification or continuation/discontinuation of the trial. The Steering Committee will review the recommendations of the Executive Committee as outlined in Figure 2. Outcomes Research will maintain the safety

database for the trial. Outcomes Research Statisticians will be responsible for the creation of the Executive Committee safety and efficacy reports and will prepare summary reports of serious adverse events, unanticipated adverse device effects, and study endpoints using blinded treatment groups for the Executive Committee.

The initial review of data by the Executive Committee will take place after at least the first **22** patients have been enrolled and randomized to treatment or control. The Executive Committee will evaluate the data in blinded fashion (e.g. Drug A and Drug B). Subsequent meetings/discussions will be held after approximately every 22 patients are randomized in this investigation. Interim analysis will be planned and pre-programmed in advance ensuring a quick-turnaround. Study recruitment may continue while the interim analysis is being performed. The Executive Committee chairperson and the full committee will determine additional reviews of the data. If necessary, the Executive Committee Chairperson can request more frequent reports.

Figure 2
Actions upon receipt of an
Executive Committee recommendation

Interpretation of safety data is very complex and requires both clinical and statistical experts reviewing the data. A number of considerations for interpretation of these data can be stated and these include:

- a) Whether the results could be explained by possible differences in the baseline variables between the groups;
- b) Whether outcomes could be biased because of the differences in treatment programs;
- c) Whether the results are consistent for other variables which should be associated with the primary outcome variables in question;
- d) Whether the results are consistent among various subgroups of patients involved in the study;
- e) Whether the risk which is under consideration is outweighed by assessment of the overall benefits of therapy;
- f) Whether results could be due to confounding factors and not due to the solution
- g) Whether it is likely that the current trends could be reversed if the trial were to be continued unmodified.

All of these considerations require expert evaluation and are the major role of the Executive Committee. The Executive Committee will consider these issues on a regular basis to assure the safety of the patients and to assure the investigators and the medical community that the risks of this study are being evaluated and the patient's safety is being kept foremost in mind. At the point where the Executive Committee believes that evidence of a meaningful difference beyond a reasonable doubt exists between treatment arms such that a specific recommendation related to alteration of the study would be made, a statistician will identify the appropriate treatment groups and the Steering Committee will be notified. The Chairperson will document the discussion with minutes and consolidate the comments of all members. Within three days following each of their meetings, the Executive Chairperson will prepare a written report for the Steering Committee outlining any serious safety concerns and explaining their recommendations. The report will typically include only blinded, pooled-group results, but the committee may release selected unblinded results if considered necessary to the Steering Committee.

Elements of the Executive Committee report may include the following:

1. Patients enrolled
2. Protocol deviations
3. Selected clinical risk/cardiac history factors
4. Selected demographic/baseline factors to include gender, race and age
5. Deaths (patient listing of events to indicate cardiac vs. non-cardiac)
6. Evidence of Kidney injury (urinary concentrations of neutrophil gelatinase-associated lipocalin (NGAL), urinary concentrations of interleukin (IL)-18, serum creatinine, need for renal replacement therapy).
7. Evidence of Coagulopathy or major bleeding (worsening of parameters of coagulation function from thromboelastometry (including the reaction time (R value), clot formation time (K value), **angle (α)**, maximum amplitude (MA), **clot lysis at 30 min (LY30)**, and coagulation index (CI) and platelet function and platelet aggregometry including platelet count, ADP-, collagen- and arachidonic acid platelet aggregation), increase in serum coagulation parameters including serum prothrombin time (PT), international normalized ratio (INR), and activated partial thromboplastin time (aPTT),

8. Evidence of liver dysfunction
9. Evidence of anaphylactoid and hypersensitivity reactions
10. Serious Adverse events

Procedures for Communicating Recommendations to the Steering Committee

Executive Committee recommendations that are voted on and passed are transmitted in writing to [name]. Chair of the Steering Committee, within three working days (or less if considered urgent) of the meeting/call at which the recommendation was formulated and passed. (Figure 2)

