^a Hespan (6% HES 450/0.7 in 0.9% Sodium Chloride Injection) is not recommended for use as a cardiac bypass pump prime, while the patient is on cardiopulmonary bypass, or in the immediate period after the pump has been discontinued because of the risk of increasing coagulation abnormalities and bleeding in patients whose coagulation status is already impaired.

- 3) **Secondary Aim 2: Safety assessment (coagulation and platelet function).** To assess the safety of HES 130/0.4 versus albumin 5% as measured by coagulation parameters and platelet function measured at baseline, within one hour of arrival to ICU (\pm 1 hour), and 24 hours (\pm 2 hours) following surgery (or within two hours prior to discharge from the ICU if patient is discharged in less than 24 hours). Additional exploratory clinical outcomes including blood loss and transfusion requirements will also be collected.
- 4) **Tertiary Aim 1: Exploratory analyses (inflammatory response).** To assess the anti-inflammatory effects of intraoperative administration of HES 130/0.4 in cardiac surgical patients measured by perioperative levels of interleukin - 6 (IL-6), tumor necrosis factor - α (TNF- α), and macrophage migration inhibitory factor (MIF), measured at baseline (following anesthetic induction and prior to surgical incision), within one hour of arrival to ICU (\pm 1 hour), and 24 hours (\pm 2 hours) postoperatively (or within two hours prior to discharge from the ICU if patient is discharged in less than 24 hours) compared with patients who received 5% human albumin.
- 5) **Tertiary Aim 2: Exploratory analysis (pulmonary function).** To examine whether intraoperative administration of HES 130/0.4 compared with 5% albumin affords benefit on postoperative pulmonary dysfunction as measured by ratio of partial arterial oxygen tension (PaO₂) to fraction of inspired oxygen (FiO₂) measured at baseline, within one hour of arrival to ICU (\pm 1 hour), and 6 hours following ICU arrival (\pm 1 hour) or within 30 min prior to initiation of Continuous Positive Airway Pressure (CPAP) weaning trial prior to extubation , whichever is earlier. Additional exploratory outcome measures including dynamic lung compliance will be assessed.

The Effects of 6% HES 130/0.4 in Cardiac Surgical Patients

BACKGROUND

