Recently, new generation HES solutions, such as HES 130/0.4 with lower molecular weight and molar substitution, have been purported to have minimal adverse effects on coagulation parameters.^{15,16} A pooled analysis which compared HES 130/0.4 with earlier generation HES found that HES 130/0.4 produced less abnormalities in coagulation, less blood loss and lower transfusion requirements compared with the earlier generation HES solutions.¹⁷ In addition, newer HES solutions have been found to inhibit the inflammatory response, which may further decrease risk of postoperative coagulopathy. However, although some investigations of the coagulation effects of HES 130/0.4 in cardiac surgical patients found minimal effect on coagulation parameters,¹⁵ conflicting evidence exists.¹⁸ Some reports found that HES 130/0.4 caused global extrinsic and intrinsic pathway coagulation abnormalities in contrast to albumin.¹⁸ In addition, a large randomized controlled trial found that HES 130/0.42 (Tetraspan) was associated with increased incidence of severe bleeding in septic critically ill patients.² Further, a recent meta-analysis of 18 randomized, controlled trials found increased risk of bleeding, blood product transfusion, and reoperation in patients who received HES solutions during cardiac surgery.⁸ This report was limited, however, by the fact that head-to-head trials comparing risk of bleeding of newer generation HES solutions, such as HES 130/0.4 with human albumin 5% have not been performed. In fact, the analysis extrapolated results from older generation HES solutions (HES 200/0.5) to the newer HES products, because no direct comparison was available. Nevertheless, because of these recent results, the FDA has added safety information, specifically, the risk of excess bleeding in cardiac surgical patients, to the Warnings and Precautions section

of the package insert of all HES products,^b irrespective of molecular weight or degree of molar substitution. Thus an investigation comparing coagulation abnormalities and bleeding between albumin and the newer HES products, namely HES 130/0.4 (Voluven) are necessary to examine the safety profile in cardiac surgical patients.

Thus, whether HES 130/0.4 (Voluven) impairs clinical and laboratory coagulation parameters compared to albumin in adult cardiac surgical patients is unclear and the clinical impact is unknown. Further investigation of the safety of HES 130/0.4 administration on coagulation parameters is needed.

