- 2) Additional coagulation measures from thromboelastography, including the **reaction time (R value)**, **clot formation time (K value)**, **angle (α)**, **maximum amplitude (MA)**, **clot lysis at 30 min (LY30)**. We will collect data on **coagulation index (CI)** and compare between groups, because it is a clinically important measurement. However, the CI is based on the components of thromboelastography (a summary variable); thus it will not be included as an outcome measure.
- 3) Assessment of **platelet function**, including platelet count, **ADP-, collagen- and arachidonic acid platelet aggregation**

Descriptive variables of transfusion, coagulation and platelet function)

- 1) Amount of cell saver administration, packed red blood cell administration, fresh frozen plasma, and platelets transfused, chest tube output during surgery and in the first 24 hours following surgery (or until ICU discharge, if the patient is discharged in less than 24 hours).
- 2) We will store blood samples for later analysis for coagulation and platelet function, possibly including measures of Factor VIII, von Willebrand's factor, thrombin time, fibrinogen, D-dimer.

Tertiary Outcome Measures

Tertiary aim #1 (exploratory analysis, inflammatory response)

To compare whether intraoperative administration of HES 130/0.4 (Voluven) versus human albumin 5% affords beneficial anti-inflammatory effects as measured by an important markers of the perioperative inflammatory response.

The **tertiary outcomes** will include serum concentrations of **IL-6, TNF- α and MIF**, important **markers of the inflammatory response**, to be measured at baseline, within one hour of arrival to ICU (\pm 1 hour), and 24 hours (\pm 2 hours) following completion of surgery (or within two hours prior to ICU discharge, if the patient is discharged in less than 24 hours).

Tertiary aim #2 (exploratory analysis, pulmonary function)

To compare whether intraoperative administration of HES 130/0.4 (Voluven) versus human albumin 5% provides beneficial effects on **postoperative pulmonary function** as measured by the **ratio of partial arterial oxygen tension (PaO₂) to fraction of inspired oxygen (FiO₂)**

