($P_aO_2:F_iO_2$ ratio) measured at baseline (following anesthetic induction), within one hour of arrival to ICU (± 1 hour), and within 30 min prior to initiation of Continuous Positive Airway Pressure (CPAP) weaning trial prior to extubation or 6 hours (± 1 hour) following completion of surgery, whichever is earlier, after end of surgery compared to patients who receive perioperative 5% human albumin.

Tertiary outcome measures of pulmonary function

1. $P_aO_2: F_iO_2$ ratio

Exploratory outcomes (pulmonary function)

2. Dynamic lung compliance
3. Gas exchange capacity, including oxygenation index and ventilation index

Dynamic lung compliance: Measurements will be performed using pressure-control mode with a driving pressure titrated to achieve a tidal volume (V_T of 6 mL/kg lean body weight), fixed positive end-expiratory pressure (PEEP) of 8 cmH₂O, respiratory rate, fraction of inspired oxygen FIO₂, and inspiratory time. Dynamic lung compliance will be calculated from the following formula:

$$\text{Dynamic compliance} = V_T / (\text{PIP} - \text{PEEP}),$$

where PIP = peak inspiratory pressure.

$$\text{Oxygenation index (OI): } OI = \text{MAP} \times FIO_2 / PaO_2$$

where MAP = mean airway pressure, FIO₂ = fraction of inspired oxygen.

$$\text{Ventilation index (VI): } VI = RR \times (\text{PIP} - \text{PEEP}) \times PaCO_2 / 1,000$$

where RR = the respiratory rate.

Additional descriptive measures will be collected at baseline and throughout the ICU course:

- 1) Peak intraoperative and postoperative serum lactic acid
- 2) Peak intraoperative and postoperative serum base excess
- 3) Weight gain

Descriptive variables (which will be reported by group) that will be collected during hospitalization or at time of hospital discharge (collected from the patient's medical record, Cardiothoracic Anesthesia Registry, Cardiovascular Information Registry), medical records from outside institutions (with patient consent) and/or the Social Security Death Index. These will be reported and compared by group for descriptive purposes.

- 1) Dose of cardiovascular inotropic and vasopressor infusions administered at end of surgery and during ICU stay, such as epinephrine, norepinephrine, milrinone.
- 2) New requirement for mechanical circulatory support following surgery
- 3) Requirement for chest re-exploration
- 4) Incidence of postoperative pulmonary effusions (diagnosed by chest X-ray or ultrasound)

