Fluid challenges may be repeated until no further increase in these parameters occurs, suggesting that fluid resuscitation has been successful and euvolemia has been achieved. Also, patients will receive fluid equivalent to that judged to be lost from surgical hemorrhage. The maximum dose of HES 130/0.4 will be 35 mL/kg/day. If further plasma volume expansion is needed, lactated Ringer's solution will be used for additional fluid boluses as required.

Transfusion of packed red blood cells and blood components

Minimum hematocrit (HCT) will be approximately 23% following cardiopulmonary bypass and 21% on cardiopulmonary bypass. If the HCT decreases below these values, packed red blood cell transfusions may be administered. Erythrocyte transfusions may be administered for hypovolemia in the setting of a low hematocrit (hematocrit < 26%) or if considered necessary by the attending anesthesiologist or surgeon. Platelets may be transfused for post-CPB clinical bleeding and/or platelet count < 100 after activated clotting time is normalized. Fresh frozen plasma and/or cryoprecipitate transfusion may occur if coagulopathy or severe clinical bleeding persists following protamine administration without evidence for usual hemostatic response, elevated prothrombin time, or elevated activated partial thromboplastin time. In addition, administration of blood component transfusion may be used in the clinical setting of coagulopathy or nonsurgical bleeding as determined by the attending surgeon and/or anesthesiologist.

Anesthetic and surgical management

Anesthetic and surgical patient care will be performed following usual Cleveland Clinic procedures, which include the use of standard ASA monitors, an arterial catheter, and a central venous or pulmonary artery catheter, and transesophageal echocardiography. Intravenous anesthetic induction may consist of etomidate or propofol with succinylcholine or a non-depolarizing muscle relaxant to facilitate tracheal intubation. Isoflurane, fentanyl, and/or midazolam will be administered for maintenance of anesthesia. Additional non-depolarizing muscle relaxant will be administered in incremental doses as clinically indicated. Patients who

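### Cryoprecipitate is permitted for post-bypass coagulopathy or severe bleeding but is missing from the list of transfused products to be recorded

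*Combined protocol and SAP*

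**What the plan says.** Two sections need to be read together.

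- **What may be given.** The section on transfusion of packed red blood cells and blood components allows red cells and platelets under stated conditions. For bleeding after bypass it adds: "Fresh frozen plasma and/or cryoprecipitate transfusion may occur if coagulopathy or severe clinical bleeding persists following protamine administration". It then leaves further use to the attending clinicians: "administration of blood component transfusion may be used in the clinical setting of coagulopathy or nonsurgical bleeding".
- **What will be recorded.** Item 1 of the descriptive variables of transfusion, coagulation and platelet function (under Secondary outcome measures 2) lists: "Amount of cell saver administration, packed red blood cell administration, fresh frozen plasma, and platelets transfused". The same item continues with "chest tube output during surgery and in the first 24 hours following surgery", or until ICU discharge if that is earlier.

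In the Specific Aims, Secondary Aim 2 is more general: "Additional exploratory clinical outcomes including blood loss and transfusion requirements will also be collected". It names no product. Statistical Methods, after describing the analysis of Secondary Aim 2, states that conclusions on safety will draw on descriptive statistics as well as on tests.

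**The concern.** The background reports that a meta-analysis of 18 randomized trials "found increased risk of bleeding, blood product transfusion, and reoperation in patients who received HES solutions during cardiac surgery". A description of transfusion by group is thus one of the places where a reader will look for a bleeding signal. The protocol names cryoprecipitate as a treatment for coagulopathy or severe bleeding that persists after protamine, but the list of recorded products leaves it out.

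Because the permission is worded as plasma, cryoprecipitate or both, cryoprecipitate can stand in for plasma. A patient who received it without plasma would contribute zero to the plasma amount, and nothing else on the list would show that a product of this kind had been given. At stake is the completeness of the descriptive transfusion comparison between HES and albumin.

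**Working it through.** No arithmetic beyond a count applies, and the plan gives no figure to reproduce. The check compares permitted products with recorded products, then looks for any other section that would capture the missing one.

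**Step 1: permitted against recorded.**

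| Donor product | Permitted (transfusion section) | Named in descriptive item 1 |
|---|---|---|
| Packed red cells | yes | yes |
| Platelets | yes | yes |
| Fresh frozen plasma | yes | yes |
| Cryoprecipitate | yes | no |

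Four donor products are permitted by name and three are listed, so 4 − 3 = 1 is missing. Cell saver blood is also listed, but it is the patient's own blood and not a donor product.

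**Step 2: is the list open?** It has no open-ended phrase that would bring in further products.

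**Step 3: is cryoprecipitate captured elsewhere?**

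- *Specific Aims, Secondary Aim 2:* refers to transfusion requirements in general. Descriptive item 1 is where that phrase is made specific.
- *Perioperative Data collection:* draws descriptive variables from the medical record and two registries, but makes no commitment to any particular blood product.
- *Table 1:* has a row for cell saver volume and none for any donor product. Its silence on cryoprecipitate therefore adds no evidence either way.
- *Elements of the Executive Committee report:* list coagulation and platelet measures and major bleeding, but no transfused products.
- *Descriptive item 2:* fibrinogen is only a possible later assay on stored blood. A level is in any case not a record of treatment.

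The transfusion section is the only place that mentions cryoprecipitate.

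**Step 4: what does the gap reach?** Item 1 is descriptive, with no noninferiority margin, significance level or stopping boundary attached. The primary NGAL analysis, the secondary noninferiority tests and the sample size do not use it. Its one formal route into the conclusions is the statement that safety will be judged partly on descriptive statistics.

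**The case against.** The strongest reply is that this is one missing word in a descriptive variable. Secondary Aim 2 promises transfusion requirements without limiting the products, the chart and registries may well hold the data, and the case report forms and operations manuals are not part of the public documents, so the field may already exist. This stands in part: the data need not be lost. But no section commits to extracting cryoprecipitate or reporting it by group, and the one section that names products leaves it out.

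The reply also rightly blocks several stronger readings that a reader might infer:

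- *That treatment of HES-related bleeding goes uncounted.* It does not. Red cells, plasma, platelets, cell saver and chest tube output are recorded in the same item, and "Requirement for chest re-exploration" is on the list of variables collected during hospitalization.
- *That a patient given cryoprecipitate would appear to have had no coagulation treatment.* That would also require that the patient had no plasma and no platelets. The documents do not say how often this happens.
- *That the comparison would show no difference, or less plasma in the arm that bleeds more.* The first would need every other recorded measure to be equal as well. The second would need substitution that differs by arm. Clinicians are blinded to the study solution, and nothing in the documents points to such substitution.
- *That the coagulation tests are invalidated.* The planned models for these outcomes do not use transfusion data. Recording cryoprecipitate would help a reader interpret the results but would not change the tests.

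**Conclusion.** The omission is real and follows from the text alone: one of four permitted donor products is not on the closed list of recorded products, and no other section commits to recording it. As written, the descriptive transfusion comparison would miss cryoprecipitate, including when it replaces plasma.

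The consequence is limited to that comparison and to whatever weight it carries in the safety conclusions. The other bleeding measures and all planned hypothesis tests are unaffected. The documents give no rates of cryoprecipitate use, so the size of the gap in patients or units cannot be stated, and the point does not depend on it. The conclusion assumes that the item is carried out as worded; if the case report form already has the field, only the protocol text needs correcting. This is a cheap completeness improvement, not a flaw in the trial's main inference.

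**What to change.** In item 1 of the descriptive variables of transfusion, coagulation and platelet function, add cryoprecipitate (in units), collected over the same window as the rest of the item: during surgery and the first 24 hours afterwards, or until ICU discharge if earlier. Add the field to the case report form if it is not there, and report it by group beside red cells, plasma and platelets.

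A Table 1 row is optional, since none of the donor products has one. If a row is wanted, it should cover all four.

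The cost is one more item to extract from the existing record. Patient care, sampling, analysis methods and sample size stay as they are.
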